8.2.2. Critical procedures performed at entry to Part B (Visit B1)

- Vital signs
- Resting 12- lead ECG
- Physical examination
- Concomitant medication review
- Exacerbation review
- Laboratory tests:
 - Chemistry (including LFT)
 - Haematology with differential
 - Urine pregnancy test- for all females of child bearing potential
- AE/SAE assessment

8.2.3. Critical procedures performed at Randomization (Visit C1)

- History of previous intubations, asthma exacerbation history in previous year, asthma triggers
- Review of randomization criteria (see Section 6.3)
- Subject/Clinician global impression of asthma severity rating
- St. George's Respiratory Questionnaire (SGRQ)
- Vital signs
- Physical examination
- Spirometry (pre- and post-albuterol/salbutamol)
- Review/Collect eDiary data
- Exacerbation review
- Smoking status
- Concomitant medication assessment
- Laboratory tests:
 - Clinical Chemistry (including LFT)
 - Haematology with differential
 - Biomarker sample
 - Urine pregnancy test for all females of childbearing potential
- AE/SAE assessment

8.3. Efficacy

8.3.1. Efficacy Endpoints

Efficacy endpoints are listed in Section 4.

8.3.2. Efficacy Assessments

The timings of all efficacy assessments are documented in the Time and Events Schedules ([Table 5](#), [Table 6](#), [Table 7](#) and [Table 8](#)).

8.3.2.1. Asthma Exacerbations

Clinically significant exacerbations of asthma are defined by:

Worsening of asthma which requires use of systemic corticosteroids¹ and/or hospitalisation and/or ED visits.

¹*For all subjects, i.v. or oral steroid (e.g., prednisone) for at least 3 days or a single IM corticosteroid dose is required. For subjects on maintenance systemic corticosteroids, at least double the existing maintenance dose for at least 3 days is required.*

Clinically significant exacerbations recorded in the eCRF by the Investigator or designee will be verified using eDiary data to confirm that the exacerbation was associated with changes in:

- AM peak flow (L/min)
- rescue medication use
- nocturnal awakening due to asthma symptoms requiring rescue medication use
- symptoms

In the case that an event described as a clinically significant exacerbation is not associated with deterioration in at least one of these objective eDiary parameters, the investigator will be asked to provide an explanation to support the decision for defining the event as an exacerbation. In those circumstances where the event cannot be supported by any objective assessment, the case will not be included as a protocol defined clinically significant exacerbation, but will be included as an investigator defined exacerbation. This verification process will be overseen by GSK clinical staff to ensure consistency. Additional details on the process for determination of clinically significant exacerbations can be found in the Reporting and Analysis Plan (RAP).

Details of each asthma exacerbation, including medications used to treat exacerbations should be recorded in the eCRF.

Asthma exacerbations should not be recorded as an Adverse Event unless they meet the definition of a Serious Adverse Event.

The time period for collection of exacerbation information in the eCRF will be from the time that the ICF is signed until the Exit Visit or EW.

8.3.2.1.1. Guideline for Assessing Multiple Exacerbations

Exacerbations which are separated by less than 7 days will be treated as a continuation of the same exacerbation.

8.3.2.2. eDiary Reporting, Worsening of Asthma and Alerts: Part B, C and D

Subjects should be instructed to bring their eDiary to each Clinic Visit in Part B, Part C and Part D.

The subject will be asked to record the following parameters **daily** in the eDiary from Visit B1 until the completion of Part C or Part D:

- Morning peak flow (best of three), before rescue medication usage (L/min).
- Asthma symptom score over the previous 24-hours using a 6-point scale ([Appendix 7](#))
- Occasions of rescue medication usage over the previous 24-hours
- Frequency of awakening due to asthma symptoms requiring rescue medication use

8.3.2.2.1. eDiary Alerts Indicating Worsening of Asthma

For safety the following alerts, indicative of worsening asthma, will be programmed into the eDiary with instructions to contact the investigator if any of the alert criteria are met.

NOTE: An alert in itself will not qualify as a clinically significant exacerbation:

- Decrease in morning PEF $\geq 30\%$ on at least two of three consecutive days, compared with baseline (last 7 days of run-in Part B)
- A symptom score of 5 for at least two of three consecutive days
- An increase of $\geq 50\%$ in occasions of rescue medication on at least two of three consecutive days, compared with the average use for the previous week.
- Awakening due to asthma symptoms requiring rescue medication use for at least two of three consecutive nights.

Sites should review subject data weekly during Part C through a study specific web portal, and contact subjects for follow-up as appropriate. Additionally, eDiary data will be reviewed at each clinic visit in Parts C and D by the site staff throughout the treatment period to confirm an association between any exacerbation event and eDiary data.

8.3.2.2.2. eDiary Daily Entry: Missed Days of Work or School

Subjects who work for pay or go to school on a regular basis will record in the eDiary any full and part days of missed work or school due to asthma.

8.3.2.2.3. eDiary Weekly Entry: Asthma Control Questionnaire-5 (ACQ-5)

Subjects in Part B, Part C and Part D should complete the ACQ-5 on their eDiary once weekly.

The ACQ-5 is a five-item questionnaire, which has been developed as a measure of subject's asthma control that can be quickly and easily completed [Juniper, 2005]. The questions are designed to be self-completed by the subject. The five questions enquire about the frequency and/or severity of symptoms over the previous week (nocturnal awakening on waking in the morning, activity limitation, and shortness of breath, wheeze). The response options for all these questions consist of a zero (no impairment/limitation) to six (total impairment/ limitation) scale.

8.3.2.2.4. eDiary Compliance

Subjects should be compliant in completing their daily eDiary entries between each pair of on-treatment visits. Subjects should be $\geq 80\%$ compliant with completion of their eDiary. Subjects who are non-compliant ($< 80\%$) should be re-educated on the requirement for daily diary entry compliance, and this re-education should be documented in the subjects source notes.

8.3.2.3. Paper Diary

Subjects will be issued a paper worksheet to record adverse events, changes in concomitant medications and any visits to the hospital and/or emergency department during the study. Subjects will be asked to bring their worksheet to every study visit as it will be used to assist subject recall in discussions with the investigator, for site staff to then enter as appropriate in the eCRF.

8.3.2.4. Spirometry

Spirometry will be performed to assess FEV₁ and FVC using the sites own equipment as detailed in the Time and Events Tables (Table 5, Table 6, Table 7 and Table 8).

The spirometer should meet American Thoracic Society standards and produce a print out of all data generated, which should be stored in the subjects source notes. The spirometer should be calibrated per manufacturer's instructions and a calibration log maintained.

At least 3 acceptable and ideally, 2 repeatable spirometry manoeuvres (from a maximum of 8 attempts) should be achieved on each occasion that spirometry assessments are performed, in accordance with the American Thoracic Society/European Respiratory Society (ATS/ERS) standards [Miller, 2005]. At each visit, spirometry assessments should be performed at the same time of day (± 2 hours) as the baseline assessment for that part of the study (i.e., the same time of day as Visit 1 for Part A, Visit B1 for Part B, Visit C1 for Part C). Subjects should withhold rescue albuterol/salbutamol for ≥ 6 hours and LABAs or ICS/LABA fixed dose combinations for ≥ 12 hours prior to spirometry, if possible.

Details on performing the spirometry assessments, as well as specific instructions on performing the spirometry manoeuvres, are documented in the SRM.

8.3.2.4.1. Pre- and Post-Albuterol/Salbutamol Spirometry

At all spirometry assessments conducted within Part B and Part C, both pre- and post-albuterol/salbutamol spirometry will be obtained.

Bronchodilator responsiveness testing will be completed as follows:

- Following pre-albuterol/salbutamol spirometry, the subject will self-administer 4 puffs of albuterol/salbutamol via MDI. Spirometry efforts should be obtained approximately 10 to 30 minutes after albuterol/salbutamol administration.

8.3.2.5. Paper-based Asthma Control Questionnaire-5 (Part A only)

Subjects in Part A of the study will complete the ACQ-5 at specified clinic visits ([Table 5](#) and [Table 6](#)) on paper, and their responses will be entered by site staff into the eCRF.

Note: In parts B, C and D the ACQ-5 will be completed by subjects using their eDiary (Section [8.3.2.2.3](#)).

8.3.2.6. St. George's Respiratory Questionnaire (SGRQ)

The St. George's Respiratory Questionnaire is a well established instrument, comprising 50 questions designed to measure Quality of Life in patients with diseases of airway obstruction, measuring symptoms, impact, and activity. The questions are designed to be self-completed by the subject, taking on average 20 minutes [[Jones, 1992](#)] with a recall over the past 4 weeks. It has been used successfully in studies of chronic obstructive pulmonary disease (COPD) and asthma subjects and has been translated and validated for use in most major languages. Research has demonstrated that it is sensitive to change, and interpretation of the results has been enhanced by determination of the score change necessary to achieve a clinically meaningful improvement in quality of life [[Jones, 2002](#)].

Additional instructions for the completion of SGRQ are provided in the SRM.

8.3.2.7. Subject/Clinician Rating of Global Impression of Disease Severity and Response to Therapy

The Global Impressions of Disease Severity and Response to Therapy should be the first procedure completed by the subject and clinician (Primary or Sub Investigators) at the specified study visit. To avoid biasing responses, the subjects should not be told the results of diagnostic tests prior to completing the questionnaires and these questionnaires should be completed before any procedures are performed on the subject to avoid influencing the subject's and Investigator's response.

Additional instructions will be found in the SRM.

Global Impression of Disease Severity: The investigator (or designee) and subject will complete a Global Impression of Disease Severity question at Randomisation and visits described in [Table 7](#). This single global question will ask subjects and clinicians to rate the subject's asthma severity on a four-point scale (mild, moderate, severe, very severe).

Response to Therapy: The investigator (or designee) and subject will also be asked to rate the subject's response to therapy at specified visits ([Table 7](#)). This is an overall evaluation of response to treatment, *as compared to Visit C1*. This will be conducted separately by the investigator (or designee) and the subject using a seven-point rating scale as follows:

- 1 = significantly improved
- 2 = moderately improved
- 3 = mildly improved
- 4 = no change
- 5 = mildly worse
- 6 = moderately worse
- 7 = significantly worse

8.3.2.8. Healthcare Resource Utilization

All unscheduled asthma-related visits to a physician's office, visits to urgent care, visits to the emergency department, and hospitalizations associated with the subject's asthma will be recorded in the eCRF.

At Visits C2 through the Part C Exit Visit or EW, the resource utilization worksheet used by the patient to record all health care contacts experienced since the last visit will be presented to the investigator (or designated coordinator). The investigator (or designated coordinator) should ask the subject if any of the health care contacts that are recorded on the worksheet were due to asthma. The investigator can refer to his/her records to verify or supplement information given by the subject, if necessary.

If any unscheduled healthcare contact is due to an asthma exacerbation, then the Asthma Exacerbation section of the eCRF must be completed.

Details regarding completion of the Healthcare Utilization worksheet are located in the SRM.

8.4. Safety

Planned time points for all safety assessments are listed in the Time and Events Tables (Section [8.1](#)).

See Section [4](#) for details of the safety endpoints to be assessed in the study.

8.4.1. Adverse Events (AE) and Serious Adverse Events (SAEs)

The definitions of an AE or SAE can be found in [Appendix 4](#).

Adverse Events include systemic (i.e., allergic/IgE-mediated and non-allergic) and injection site reactions reported throughout all study treatment periods. If the investigator considers that there is a reasonable possibility that the Systemic reaction (e.g., Hypersensitivity) or Local injection site reaction event is related to investigational product, then additional information about the type of reaction and whether it meets anaphylaxis criteria will be collected in the eCRF.

NOTE: Hypersensitivity reactions will be monitored using the diagnostic criteria for anaphylaxis as outlined by the 2006 Joint NIAID/FAAN Second Symposium on Anaphylaxis [Sampson, 2006] ([Appendix 8](#)). Information will be also collected from subjects to help with the assessment of potential localised injection site reactions.

The investigator and their designees are responsible for detecting, documenting and reporting events that meet the definition of an AE or SAE.

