
Risk of Systemic Allergic and Non-allergic Reactions, including Anaphylaxis
	
Biopharmaceutical products administered subcutaneously may elicit systemic (e.g. hypersensitivity) and local site reactions.
 
Reactions reported to date across the mepolizumab program are summarized in the IB; see ‘Special Warnings and Special Precautions for Use’ section located in Section 6 titled ‘Summary of Data and Guidance for the Investigator’.
	
Daily monitoring of serious adverse events (SAEs) by medical monitor; regular systematic review of adverse event (AE)/SAE data from ongoing studies by a GSK safety review team.
 
Specific case report form (CRF) pages utilized for targeted collection of reactions data.
 
Use of Joint NIAID/FAAN 2nd Symposium on Anaphylaxis to collect data on reports of anaphylaxis (see Appendix 8).
 
Safety monitoring of subjects is required during SC administration, in accordance with standard of care at the site.

Risk of Immunogenicity
	
Biopharmaceutical products may elicit anti-drug antibody (ADA) and neutralizing antibody (NaB), which have the potential to modulate pharmacokinetic (PK), pharmacodynamic (PD) or produce adverse reactions. However, humanized and fully human antibodies are less immunogenic than mouse or chimeric monoclonal antibodies.
 
Immunogenicity data reported to date across the mepolizumab development program are summarized in the IB; See ‘Clinical
	
Blood samples are collected in clinical studies for detection of both ADA and NaB.
 
Monitoring of subjects for immunogenic-related events will be done by the treating physician as per standard of care.
 
Immunogenicity profile will be updated in the Mepolizumab IB as appropriate.

Potential Risk of Clinical Significance	Summary of Data/Rationale for Risk	Mitigation Strategy
	Immunogenicity' and a summary of immunogenicity findings in the 'Other Potentially Clinically Relevant Information for the Investigator' section titled 'Summary of Data and Guidance for the Investigator'.	

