13.4.5. Evaluating AEs and SAEs

Assessment of Intensity

The investigator will make an assessment of intensity for each AE and SAE reported during the study and will assign it to one of the following categories:

- Mild: An event that is easily tolerated by the subject, causing minimal discomfort and not interfering with everyday activities.
- Moderate: An event that is sufficiently discomforting to interfere with normal everyday activities
- Severe: An event that prevents normal everyday activities. - an AE that is assessed as severe will not be confused with an SAE. Severity is a category utilized for rating the intensity of an event; and both AEs and SAEs can be assessed as severe.
- An event is defined as 'serious' when it meets at least one of the pre-defined outcomes as described in the definition of an SAE.

Assessment of Causality

- The investigator is obligated to assess the relationship between study treatment and the occurrence of each AE/SAE.
- A "reasonable possibility" is meant to convey that there are facts/evidence or arguments to suggest a causal relationship, rather than a relationship cannot be ruled out.
- The investigator will use clinical judgment to determine the relationship.
- Alternative causes, such as natural history of the underlying diseases, concomitant therapy, other risk factors, and the temporal relationship of the event to the study treatment will be considered and investigated.
- The investigator will also consult the Investigator Brochure (IB) and/or Product Information, for marketed products, in the determination of his/her assessment.
- For each AE/SAE the investigator **must** document in the medical notes that he/she has reviewed the AE/SAE and has provided an assessment of causality.
- There may be situations when an SAE has occurred and the investigator has minimal information to include in the initial report to GSK. However, **it is very important that the investigator always make an assessment of causality for every event prior to the initial transmission of the SAE data to GSK.**
- The investigator may change his/her opinion of causality in light of follow-up information, amending the SAE data collection tool accordingly.
- The causality assessment is one of the criteria used when determining regulatory reporting requirements.

Follow-up of AEs and SAEs

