13.8. Appendix 8: Anaphylaxis Criteria

Joint NIAID/FAAN Second Symposium on Anaphylaxis [[Sampson, 2006](#)]. The criteria do not make a distinction based on underlying mechanism. These criteria are summarized as follows:

- 1) Acute onset of an illness (minutes to several hours) with involvement of the skin, mucosal tissue, or both (e.g., generalized hives, pruritus or flushing, swollen lips-tongue-uvula), and at least one of the following:
 - a) Respiratory compromise (e.g., dyspnea, wheeze-bronchospasm, stridor, reduced PEF, hypoxemia)
 - b) Reduced blood pressure (BP) or associated symptoms of end-organ dysfunction (e.g., hypotonia [collapse], syncope, incontinence)
- 2) Two or more of the following that occur rapidly after exposure to a likely allergen for that patient (minutes to several hours):
 - a) Involvement of the skin-mucosal tissue (e.g., generalized hives, itch-flush, swollen lips-tongue-uvula)
 - b) Respiratory compromise (e.g., dyspnea, wheeze-bronchospasm, stridor, reduced PEF, hypoxemia)
 - c) Reduced BP or associated symptoms (e.g., hypotonia [collapse], syncope, incontinence)
 - d) Persistent gastrointestinal symptoms (e.g., crampy abdominal pain, vomiting)
- 3) Reduced BP after exposure to known allergen for that patient (minutes to several hours):
 - a) Infants and children: low systolic BP (age specific) or greater than 30% decrease in systolic BP
 - b) Adults: systolic BP of less than 90 mm Hg or greater than 30% decrease from that person's baseline

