#### 8.1.1. Adverse Events of Special Interest Analyses

Adverse events of special interest (AESIs) for closer monitoring are listed in Section [11.6.4](#).

Separate summary tables showing the number and percent of subjects with each type of AESI, broken down by preferred term will be created. Information will be reported as part of the standard AE tables for AESIs of infections, serious infections, neoplasms, cardiac disorders and serious cardiac disorders.

For each type of AESI a profile summary table will be produced containing information which would include, but not be limited to, the number of occurrences of the event, event characteristics, time to onset, intensity, outcome and action taken.

A listing of any subjects with systemic events identified by the investigators as meeting the criteria for anaphylaxis as outlined by the 2006 Joint National Institute of Allergy and Infectious Disease/Food Allergy and Anaphylaxis Network Second Symposium on Anaphylaxis [[Sampson, 2006](#)] will be provided

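### Protocol 8.4.1 makes eCRF recording of anaphylaxis-criteria status conditional on suspected relatedness, and other text does not; read literally, the SAP's anaphylaxis displays can omit criteria-meeting reactions judged unrelated

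*Protocol*

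**What the plan says.** Protocol 8.4.1 gives the one explicit rule for when criteria status is recorded. Its condition is "If the investigator considers that there is a reasonable possibility that the Systemic reaction (e.g., Hypersensitivity) or Local injection site reaction event is related", meaning linked to the study drug, and its consequence is "then additional information about the type of reaction and whether it meets anaphylaxis criteria will be collected in the eCRF". Protocol 13.4.5 explains that a reasonable possibility means there are "facts/evidence or arguments to suggest a causal relationship, rather than a relationship cannot be ruled out".

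Other text is unconditional:

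- The NOTE in 8.4.1 says "Hypersensitivity reactions will be monitored using the diagnostic criteria for anaphylaxis".
- Table 3 in Protocol 5.6.1, against its first-listed risk of systemic reactions including anaphylaxis, cites CRF "pages utilized for targeted collection of reactions data".
- SAP 11.6.4 says that systemic reactions, including those meeting the anaphylaxis criteria, come from targeted eCRF pages.
- SAP 11.11.7 asks for a relatedness column in Listings 23 (systemic reactions) and 24 (local reactions). Its programming notes for Listing 22 (anaphylaxis) do not.

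On reporting, SAP 8.1.1 promises "A listing of any subjects with systemic events identified by the investigators as meeting the criteria for anaphylaxis". On causality, Protocol 13.4.5 states: "The investigator is obligated to assess the relationship between study treatment and the occurrence of each AE/SAE".

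**The concern.** The Appendix 8 criteria are a clinical case definition, and Appendix 8 itself notes: "The criteria do not make a distinction based on underlying mechanism". Recording whether a reaction meets them only when the investigator already suspects the product puts attribution ahead of classification. Attribution can be difficult here: bronchospasm is one element of the criteria, and every subject has severe asthma.

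The condition can only lower the count of criteria-meeting events or leave it unchanged. For a rare event, that makes a zero in Table 3.76 ambiguous. It could mean that no event met Appendix 8, or only that no event judged related did. At stake is the completeness of a descriptive count for the first risk listed in Table 3. No efficacy result is touched.

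**Working it through.** The plan gives no figure to reproduce, and the documents give no count of reactions judged unrelated. The check is a comparison of texts.

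1. **Is collection conditional?** In the 8.4.1 sentence, yes. Under 13.4.5, a case where a link merely cannot be excluded falls below the bar, so doubtful cases can fall outside the rule.

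2. **Does other text remove the condition?** Not expressly. The 8.4.1 NOTE says that hypersensitivity reactions are monitored against the criteria. Table 3 says that the criteria are used in collecting data on anaphylaxis reports and that targeted pages exist. SAP 11.6.4 names those pages as the data source. None of these states that criteria status is recorded when the event is judged unrelated, and none excludes it. The relatedness column in Listings 23 and 24 would have little purpose unless unrelated reactions were expected there. The texts therefore point in different directions.

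3. **Which displays rest on the item?** There is a summary and a profile table for each reporting period: 3.21/3.22 (Parts A/B), 3.76/3.77 (Part C) and 3.127/3.128 (Part D). Listing 22 is added to these. The count is 2 × 3 + 1 = 7 displays.

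4. **Is there a second route into those displays?** No. SAP 11.6.4 finds opportunistic infections, malignancies, serious cardiac, vascular and thromboembolic events and serious ischemic events from a preferred-term list. For systemic reactions it uses preferred terms only to divide events already captured on the eCRF into allergic and non-allergic.

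5. **Is the condition needed to separate related events?** No. Causality is assessed for each event under 13.4.5, and SAP 11.4.4.1 derives drug-related status from that assessment.

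6. **What remains visible elsewhere?** Events judged unrelated still enter the general AE and SAE tables, such as Table 3.54. Protocol 13.4.4 directs the investigator to record a diagnosis in place of individual signs where one can be reached, so a diagnosed anaphylaxis should appear under that term. An undiagnosed event coded as, say, urticaria or hypotension would appear there but could not be recognised as meeting Appendix 8.

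**The case against.** The strongest reply has four parts.

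- **The eCRF decides the matter, and it is not among the documents.** The unconditional text and the relatedness column suggest that the pages are open to unrelated reactions. This stands: an actual omission is not established.
- **Serious cases are caught anyway.** A diagnosed anaphylaxis is coded as such. Many such events would also be SAEs, which are reported within 24 hours and listed individually. This also stands, and it confines the unrecognised events to undiagnosed, symptom-coded ones.
- **Table 3 frames the risk as a product effect, so limiting extra detail to plausibly related reactions is defensible.** It is. But causality is recorded separately, so an all-cause count with a relatedness column gives both views, and the restricted count gives only one.
- **A preferred-term table would not cure the problem.** Correct: such a table cannot show which events met Appendix 8.

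A reader might infer that the plan gives no basis at all for assessing unrelated reactions against the criteria, or that the anaphylaxis displays are restricted to related events. The documents support neither. The 8.4.1 NOTE, Table 3 and SAP 11.6.4 are unconditional, and the displays depend on the investigator's identification of criteria, not on relatedness as such.

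**Conclusion.** The point holds as an inconsistency with a possible consequence. Followed literally, 8.4.1 lets seven planned displays omit a systemic reaction that meets Appendix 8 but was judged unrelated. This rests on two assumptions: that the eCRF follows the conditional sentence, and that at least one such reaction occurs. Neither can be confirmed from the documents, so the size is unknown and may be zero.

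A reader might also suspect a distorted comparison between arms. The documents give no ground for that, because Part C causality judgements are made blind to treatment. This is a cheap improvement of low priority.

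**What to change.** In Protocol 8.4.1, replace the conditional sentence for systemic reactions with: *For every systemic reaction, whether or not considered related to investigational product, the type of reaction and whether it meets the Appendix 8 anaphylaxis criteria will be recorded in the eCRF; causality is recorded separately.* If the eCRF already works this way, only the wording needs aligning.

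In SAP 11.11.7, add to Listing 22 the relatedness column already specified for Listings 23 and 24.

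The cost is one protocol sentence, one listing column and a few more completed pages on an existing form. The count will then include some reactions with other causes, which the new column identifies.

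If collection can no longer be changed, a by-arm count from a fixed anaphylaxis/hypersensitivity preferred-term list, regardless of relatedness, is an optional fallback beside the investigator-defined tables. It uses AE data already collected, but it does not establish which events met Appendix 8.
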